5.2 Protocol Deviations

During database cleaning, the unblinded SDTM data will be provided to Sponsor and to two Profil statisticians. This will still maintain the blinding as those individuals with access to the dataset will not be involved in the data base release (DBR) meeting. The statistical analysis will be provided on unblinded data before DBR.

Deviations from the protocol will be assessed as “important” or “non-important” in agreement with the sponsor. Protocol or procedure deviations are defined as “important” if they are likely to affect the outcome of the trial (e.g. effect on target variables). All other protocol and procedure

Statistical Analysis Plan				
Trial ID	EudraCT-No.	Date	Status / Version-No.	Page
I8B-MC-ITST	2019-003493-13	15 Jul 2020	Final 1.0	28 of 47

deviations are regarded as non-important. For important protocol and procedure deviations a description will be given in the CSR.

The subjects or observations to be excluded and the reason for their exclusion will be documented. Lilly's SOP for data exclusion will be followed. A sensitivity analysis may be conducted to assess the impact of data exclusion on the analysis. The reason for exclusion of subjects and details of the sensitivity analysis will be described in the CSR.

Subjects withdrawn from the trial will be listed including the primary reason for withdrawal.

In any case all decisions to correct or exclude values must have a reasonable foundation and must be documented in the meeting minutes.

New NTFs, protocol and procedure deviations may be written after the meeting as a result of findings and decisions during the DBR meeting.

The blinded review is completed after signing the DBR meeting minutes prior to database lock.

5.3 Coding

AEs, medical history, and concurrent conditions will be coded using MedDRA as described in the Data Management Plan.

Concomitant medication will be coded using the drug record number from the World Health Organization (WHO) dictionary.

The used version numbers will be documented in the database.

5.4 Missing, Unused and Spurious Data

All available data will be included in data listings and tabulations. Unless otherwise specified in Section 4, no imputation of values for missing data will be performed. Imputed values will be presented in data listings and will be flagged.

Missing statistics will be presented as "NC" (not calculable). For example, if individual values are 0, the geometric mean cannot be calculated and will be presented as "NC".

Variable specific information for imputing missing data is given in Section 4.

Statistical Analysis Plan				
Trial ID	EudraCT-No.	Date	Status / Version-No.	Page
I8B-MC-ITST	2019-003493-13	15 Jul 2020	Final 1.0	29 of 47

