08:00 hours on Day 1, a standard liquid meal [REDACTED] will be provided. No bolus insulin will be administered with the aim to induce postprandial hyperglycemia (PG > 240 mg/dL). On-site glucose measurements [REDACTED] will be performed regularly and frequently after meal ingestion. As soon as a glucose measurement above the high glucose threshold (PG > 240 mg/dL) has been measured and the result has been confirmed by a second measurement, a correction bolus will be administered with the aim to bring the subject's glucose level down to $PG \leq 140$ mg/dL. Regular and frequent sampling for glucose on-site analysis continues and the time to reach the euglycemic range threshold will be documented. PK and glucose measurements will be collected until 5 hours after administration of the correction bolus. In case $PG < 54$ mg/dL, hypoglycemia rescue will be provided. In case $PG > 306$ mg/dL for more than one hour, hyperglycaemia rescue will be provided. Thereafter, subjects will receive a free-choice lunch and a pre-defined evening meal covered by the subject's usual bolus dose.

Day 1 / Day 2: recovery from hyperglycemia after basal insulin suspension

After the insulin bolus given with the evening meal, no correction boli should be given subcutaneously. Overnight, the basal insulin infusion rate will be running and a target fasting plasma glucose level in the range of 126 ± 20 mg/dL will be aimed for. The basal insulin infusion rate will be fixed to a single hourly rate from at least – 3 hours prior to basal insulin suspension. Basal insulin suspension will be performed between 8 and 10 hours after the dinner meal on Day 1. On-site glucose measurements [REDACTED] will be performed regularly and frequently to follow the rise in plasma glucose concentration above 240 mg/dL and blood samples for PK analysis will be taken to analyse the decline in circulating insulin levels. As soon as a glucose measurement above the high glucose threshold has been measured and the result has been confirmed by a second measurement a correction bolus will be administered via a subcutaneous injection in the periumbilical region using an insulin syringe. In addition, a plasma sample for ketone concentration will be taken during this time. Regular and frequent sampling for PK, ketone and glucose analysis continues and the time to reach a $PG \leq 140$ mg/dL will be documented.

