4.3 Assessments for Pharmacodynamics

Eli Lilly will be responsible for the derivation of the PD endpoints and will provide the derived PD endpoints to Profil Institut für Stoffwechselforschung GmbH, Neuss, Germany.

For each study day (Day 1: meal test procedure with missed meal bolus and Day 2: basal insulin suspension), the primary endpoint time to recovery from hyperglycemia after administration of a correction bolus will be determined per subject and period. The determination of the time to recovery after administration of a correction bolus will be calculated from the time of correction bolus administration until the time of the exact point of time when PG is 140 mg/dL, which will be determined using linear interpolation.

Similarly, for each study day, the key secondary PD endpoints include: glucose AUCs, PG_{max} and rate of change in PG will be determined.

The secondary endpoint rate of change in PG will be defined as the change in PG at the time of bolus IMP administration (B) to PG at 140 mg/dl divided by the duration of time for this interval, based on individual measurements per subject, period and day.

The following secondary GD AUCs will be calculated per patient, period and day:

- the area under the PG curve, but above 140 mg/dL from time of correction bolus to the time that the PG is 140mg/dl ($AUC_{B-1PG140}$) and

Statistical Analysis Plan				
Trial ID	EudraCT-No.	Date	Status / Version-No.	Page
I8B-MC-ITST	2019-003493-13	15 Jul 2020	Final 1.0	20 of 47

- the area under the PG curve but above 180mg/dL from time of the correction bolus to the time that the PG is 180mg/dl ($AUC_{B-tPG180}$).

The AUCs will be calculated using the linear trapezoidal rule and using the actual times along with the time when PG is 140 mg/dL or 180mg/dL, which will be determined using linear interpolation. Additionally, calculation of baseline corrected AUC (iAUCs) using the PG at the administration time of the correction bolus may be explored to address possible inter-occasion variability.

The secondary GD endpoint PG_{max} will be determined individually per subject, period and day based on measured PG values.

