5 STATISTICAL METHODOLOGY

5.1 Analysis Sets

The following analysis sets are defined in accordance with the International Council for Harmonisation (ICH)-E9 guidance (1):

Full Analysis Set (FAS)

The full analysis set (FAS) is based on the intention-to-treat principle and includes all subjects who were randomised. Subjects will contribute to the evaluation ‘as randomised’. PK and PD listings (subjects, who are in the FAS, but not in the mFAS will be identified) and the subject disposition and demographic and baseline characteristics will be based on the FAS.

Modified FAS (mFAS)

The modified FAS includes all subjects of the FAS who complete the study according to the sequence/treatment to which they are randomised. Subjects will contribute to the evaluation ‘as randomised’. Primary and secondary statistical analyses of PK and GD parameters will be conducted on the set of subjects who complete all treatment periods with the same dose and meal intake as the PK parameters and GD response are dependent on the insulin dose which is individualized by subject.

Safety Analysis Set (SFAS)

The safety analysis set includes all enrolled subjects that have received IMP at least once (basal rate) - whether or not they fulfilled all protocol requirements. Subjects in the safety set will contribute to the evaluation ‘as treated’. The safety analysis will be based on the safety analysis set.

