5.7 Analysis of Primary Endpoints Time to Recovery from Hyperglycaemia

The PD parameters will be determined and analyzed using software SAS Version 9.4.

Subjects who did not keep identical insulin lispro doses for LY900014 and Humalog[®] for each day and period or had differences in the consumption of the test meal will be excluded from the statistical analysis of the PD parameters. Additionally, subjects which required a rescue insulin dose during the treatment assessment period would be excluded in the analysis for both treatments (LY900014 and Humalog) periods for that day (missed bolus following meal or basal insulin suspension) since an accurate comparison of the treatment difference would not be possible. Subjects excluded from the analysis will be identified by Lilly.

Statistical Analysis Plan				
Trial ID	EudraCT-No.	Date	Status / Version-No.	Page
18B-MC-ITST	2019-003493-13	15 Jul 2020	Final 1.0	31 of 47

For the primary endpoint, comparison between the treatments will be performed per day (Day 1: meal test procedure with missed meal bolus, Day 2: basal insulin suspension) using a linear mixed model analysis of variance (ANOVA) with raw endpoint as response, treatment, period and sequence as fixed effects and subject within sequence as a random factor.

Within the model, least squares means of LY900014 and Humalog[®], differences in LS-means and the corresponding 95% CI for the treatment difference will be estimated. The p-value on the difference between LS-means will be used to determine statistical significance. The treatment ratio and 95% CI for the ratio will be calculated using Fieller's theorem [4].

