APPENDIX 2 – ASSESSMENT SCHEDULE (FOR VISITS 2 AND 3)

Approx. hour	Nominal timing	Activity	Insulin (PK)	Plasma glucose ¹	Other
Day -1 17:00		Subject arrives at the trial site and continued eligibility will be checked		X	Dosing visit exclusion criteria, AEs, concomitant medication, alcohol breath test, vital signs, ECG, physical examination, urine pregnancy test, weight ⁴
17:30		Randomization (Visit 2 only) Discontinue subject's own insulin pump if not using Medtronic 640G; insert new infusion set; Start study insulin pump with IMP (subject's usual basal rate)			
18:00		Pre-defined evening meal Covered by individual meal bolus		X	
Day 1 04:00		START overnight stabilisation i.v. insulin glulisine or glucose infusion (if needed) Morning plasma glucose target (126 ± 20 mg/dL) ⬇		Sampling approx. every 30 min. or more frequently, if needed	
05:00		Fixed basal rate (single hourly rate) of CSII from at least -3 h until end of meal test (B + 5 h) ⬇		⬇	
07:30	-30 min	STOP i.v. insulin or glucose infusion (if any) Maintain PG at in the range of 126 ± 20 mg/dL			
Day 1 08:00	0	Standard liquid meal	X (pre-meal)	X (pre-meal)	Dosing visit exclusion criteria, AEs, concomitant medication
	15min	Liquid meal fully consumed		X	
	30min	Plasma glucose measurement: every 10 minutes if $PG \leq 200$ mg/dL and every 5 minutes if $PG > 200$ mg/dL ⬇		X ⬇	
	B ²	Confirmatory glucose measurement if $PG > 240$ mg/dL, followed by pump correction bolus	X ³	X ³	
	B + 5min		X	X	
	B + 10min		X	X	
	B + 15min		X	X	
	B + 20min		X	X	
	B + 25min		X	X	

Statistical Analysis Plan				
Trial ID	EudraCT-No.	Date	Status / Version-No.	Page
I8B-MC-ITST	2019-003493-13	15 Jul 2020	Final 1.0	46 of 47

Approx. hour	Nominal timing	Activity	Insulin (PK)	Plasma glucose ¹	Other
	B + 30min	As soon as PG ≤ 140 mg/dL is measured, a confirmatory PG is performed	X	X	
	B + 35min		X	X	
	B + 40min		X	X	
	B + 45min		X	X	
	B + 50min		X	X	
	B + 55min		X	X	
	B + 1h		X	X	
	B + 65min			X	
	B + 70min		X	X	
	B + 75min			X	
	B + 80min			X	
	B + 85min			X	
	B + 90min		X	X	
	B + 95min			X	
	B + 100min			X	
	B + 105min		X	X	
	B + 110min			X	
	B + 115min			X	
	B + 2h	If PG > 140 mg/dL, PG sampling will continue every 5 minutes If PG ≤ 140 mg/dL, PG sampling will be every 15 minutes	X	X	
	(B + 125 min)	If PG > 140 mg/dL		(X)	
	(B + 130min)	If PG > 140 mg/dL		(X)	
	B + 135min		X	X	
	(B + 140min)	If PG > 140 mg/dL		(X)	
	(B + 145min)	If PG > 140 mg/dL		(X)	
	B + 150min		X	X	
	(B + 155min)	If PG > 140 mg/dL		(X)	

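### An unrescued period still above 140 mg/dL at 5 hours has no primary value and drops out of the primary analysis because of its outcome; the size and direction of the bias are unknown

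*SAP*

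**What the plan says.** SAP 4.3 runs the primary endpoint from the correction bolus "until the time of the exact point of time when PG is 140 mg/dL, which will be determined using linear interpolation". SAP 3.1 limits observation on Day 1: "PK and glucose measurements will be collected until 5 hours after administration of the correction bolus". Protocol 8.8.3 and Table 3 set the same 5-hour limit on Day 2.

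The schedule allows for late crossings. From 2 hours after the bolus, SAP Appendix 2 says "If PG > 140 mg/dL, PG sampling will continue every 5 minutes", with conditional samples up to 295 min.

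SAP 5.7 analyses the time with a "linear mixed model analysis of variance (ANOVA) with raw endpoint as response", separately by day. It removes subjects with unequal doses or meals, and also rescued subjects: "subjects which required a rescue insulin dose during the treatment assessment period would be excluded in the analysis for both treatments". SAP 5.1 bases the primary analysis on the "set of subjects who complete all treatment periods with the same dose and meal intake".

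On missing values, SAP 5.4 says "Unless otherwise specified in Section 4, no imputation of values for missing data will be performed". The only imputation in Section 4 is for adverse event dates and times (SAP 4.5.1). SAP 5.2 adds "A sensitivity analysis may be conducted to assess the impact of data exclusion on the analysis".

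**The concern.** Interpolation needs a measurement on each side of 140 mg/dL. A subject still above that level at 5 hours has none below it, so the period has no primary value.

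Such a subject need not have been rescued. Protocol 8.8.1 ties extra insulin to PG above 306 mg/dL for more than an hour, or to investigator judgement, so a subject between 140 and 306 mg/dL can reach 5 hours without any. That subject may also have completed both periods with the same dose and meal. No exclusion rule applies, and the period simply contributes nothing to the fit.

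The value is then missing because recovery was slow, which is the quantity being compared. At stake are the size of the primary treatment difference and the power to detect it. If the two formulations differ in variability, the direction of the error is at stake too. The treatment of these periods is also unwritten, while the sponsor team that derives the endpoint and identifies exclusions is unblinded (SAP 4.3, 5.7 and 5.18).

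**Working it through.** **1. Inputs from the documents.** Difference 32 min, SD 78 min, a crossover mean square error of about 55, 24 completers, 80% power (SAP 3.3); two-sided alpha 0.05 (SAP 5.5.2); observation limit 5 x 60 = 300 min.

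**2. The plan's own figure.** 78/sqrt(2) = 55.15, so the 55 is on the SD scale.
- As the SD of the paired difference: SE = 55/sqrt(24) = 11.2; power = Phi(32/11.2 - 1.96) = 81% (77.8% with a t test on 22 df). The stated 80% reproduces under the normal approximation.
- As the within-subject SD, so that the SD of the difference is 78: SE = 78/sqrt(24) = 15.9; power = 52% (48.5% with t).

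Both readings are carried below as between/within-subject SDs of 39/39, 67.5/39 and 55/55. The first two give a difference SD of 39 x sqrt(2) = 55.2, the third 55 x sqrt(2) = 77.8.

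**3. Assumptions.** The documents give no mean recovery time, so slower-arm means of 120 to 210 min are assumed. Humalog is taken as slower only for illustration. Times are normal with a floor of 25 min, and nobody is rescued.

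**4. Share not recovered.** P(T > 300) = 1 - Phi((300 - mean)/SD). At mean 180 and SD 78: 1 - Phi(1.54) = 6.2% in the slower arm. With mean 180 - 32 = 148: 1 - Phi(1.95) = 2.6% in the faster arm.

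**5. Equal variability.** A random-intercept mixed model was fitted to periods with T <= 300, then to all periods with longer times set to 300. Both were compared with the full-data difference (-27 to -32 min because of the floor). Ranges cover the three SD readings.

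| Slower-arm mean (min) | Slower arm not recovered | Understated by dropping (min) | Understated by setting to 300 (min) |
|---|---|---|---|
| 120 | 0.05-1.1% | 0.1-1.1 | 0.0-0.2 |
| 150 | 0.3-2.7% | 0.3-2.3 | 0.1-0.6 |
| 180 | 1.5-6.3% | 1.2-4.3 | 0.2-1.4 |
| 210 | 5.2-12.4% | 3.3-7.0 | 0.9-2.8 |

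Power at n = 24 (full data / dropped / set to 300):

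| SDs | Mean 120 | Mean 150 | Mean 180 | Mean 210 |
|---|---|---|---|---|
| 39/39 | 76.7/76.6/76.7 | 77.9/77.0/77.9 | 77.9/75.2/77.9 | 77.9/68.7/77.5 |
| 67.5/39 | 72.3/69.9/72.0 | 75.4/70.6/74.8 | 76.7/67.5/75.6 | 77.5/60.8/75.0 |
| 55/55 | 46.3/44.2/46.2 | 47.8/42.8/47.5 | 48.0/38.2/47.5 | 48.6/33.0/47.1 |

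With no true difference, dropping gave a bias of at most 0.05 min and a type I error of 4.6 to 5.4%. At mean 180, at least one non-recovered period occurs in 33%, 83% and 86% of trials for the three SD readings in turn.

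**6. Unequal variability** (slower mean 180, correlation 0.5).

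| SD slower/faster | True shift (min) | Full data | Dropped |
|---|---|---|---|
| 78/78 | 32 | -30.7 | -26.4 |
| 65/78 | 32 | -30.1 | -30.3 |
| 55/78 | 32 | -30.1 | -32.6 |
| 60/90 | 32 | -28.5 | -33.7 |
| 55/78 | 0 | 0.5 to 0.7 | -6.3 to -6.6 |

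The last row gives two independent runs. At 65/78 the slower arm still loses more periods (3.2% against 2.6%), yet the attenuation is gone.

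**7. Skewed times.** With lognormal times (mean 180, SD 78), dropping understates by 6.5 to 8.3 min, setting to 300 by 3.5, and a right-censored model by 2.1 to 2.2.

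**The case against.** **Such periods may be rare.** This stands as a limit on size. The conditional samples let a late crossing be timed; they do not show that non-recovery at 5 hours is expected. Protocol 5.7 regards the Day 1 bolus as adequate for the meal, Protocol 5.4 lets doses be revised if they prove insufficient, and the investigator may give extra insulin. But Protocol 5.4 also foresees insufficient boli, and no expected recovery time shows that the case can be ignored. At means of 120 to 150 min the bias is small against a standard error of 11 to 16 min.

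**Day 2 may hardly be affected.** Protocol Table 3 provides an additional bolus at 2 hours if PG exceeds 180 mg/dL. If that counts as rescue, SAP 5.7 removes many slow subjects. Day 2 was not simulated.

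**A sensitivity analysis is allowed.** It is optional, concerns excluded data and names no method.

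**Stronger readings that the documents do not support.** A reader might infer that the SAP has a rule to discard slow subjects. It has none: the loss follows from the endpoint definition together with SAP 5.4, and the sponsor's data-exclusion SOP is not available here. A reader might also infer that the bias always runs toward zero and is therefore harmlessly conservative. That needs similar variability in both arms, and the SAP gives a single SD with nothing by treatment. Nor do the documents show that a false claim is likely; that too depends on unequal variability.

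**Conclusion.** The gap is real and lies in the primary analysis. Followed as written, the plan omits an unrescued period observed to 5 hours with PG still above 140 mg/dL, and omits it because of its outcome.

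With similar variability in both arms, the cost is an understated difference (0.1 to 7.0 min over assumed means of 120 to 210 min with normal times) and lost power (0.1 to 16.7 points, the largest being 77.5 - 60.8). With different variability the bias can disappear, reverse, or arise without a true mean difference. Which case applies cannot be told from the documents, so size and direction are both unknown, and the effect is negligible if few subjects exceed 5 hours. The figures rest on assumed means, the SD readings above and no rescue, and they speak mainly to Day 1.

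The change is still worth making. It is nearly free, and setting these periods to 300 min was at least as close to full data as dropping them in every scenario compared.

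**What to change.** In SAP 4.3 and 5.7:

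- Define the primary endpoint as time to PG 140 mg/dL restricted to 300 min, and label the result a restricted-time difference.
- Set to 300 only unrescued periods observed through 5 hours with PG still above 140 mg/dL and never at or below it. Periods cut short for other reasons, such as pump or catheter failure or termination for hypoglycaemia, do not receive 300.
- Add one supportive mixed model with right-censoring at 300 min (Tobit).
- Report the numbers not recovered and the numbers rescued, by treatment and day.
- State how the PG area above 140 mg/dL and the rate of change in PG are handled for the same periods, since both also need the crossing.

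Separately, the additional-bolus passages in Protocol Table 3 and Protocol 8.8.1 must be reconciled, and SAP 5.7 should say whether the Table 3 bolus counts as a rescue insulin dose.

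The cost is SAP wording and one extra model; no new data are needed. The restricted difference is usually slightly conservative for the unrestricted one (0.0 to 2.8 min in the 12 equal-variance normal scenarios). The Tobit model came within 0.1 min of full data there but relies on normality. Pairs excluded for rescue are not addressed: if half of the affected subjects are rescued (mean 180, SDs 55/55), full data give -30.7, dropping the rest -27.1 and setting the rest to 300 -28.6, so 28.6 - 27.1 = 1.5 of the 30.7 - 27.1 = 3.6 min lost is recovered.

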5.5 Presentation of Results

5.5.1 Presentation of Summary Statistics and Individual Data

In general, continuous endpoints are summarized by the arithmetic mean, geometric mean, median, standard deviation, coefficient of variation (CV), geometric coefficient of variation, and minimum and maximum. Categorical variables will be presented using descriptive summary statistics including number of subjects and percentages. Percentages of subjects will be based on non-missing values.

All PK and PD endpoints will be summarised by treatment (LY900014 and Humalog) and dosing day (Day 1 and 2) using descriptive statistics and will be provided by Lilly using their SOP. All summary PD and PK parameters and mean plots will be presented for all subjects in the mFAS, which is reflective of the subjects used in the statistical analysis.

Individual PK and PD profiles will be plotted by treatment and dosing day. Individual profiles will be presented for all available data (FAS). Similarly, individual listing of PK and GD parameters will be presented for all subjects. The presentation of individual profiles and listings will be provided in the appendix of the CSR.

The safety endpoint and all tolerability assessments will be summarised using frequency tables or descriptive statistics and will be provided by Profil. For numeric data, individual as well as minimum and maximum values will be presented with the same number of decimal places as the raw data. Descriptive statistics, such as arithmetic mean and median values will be presented with an additional decimal place and standard deviation data with two additional decimal places as the raw data.

